We propose a longitudinal, interventional, case-crossover study design to examine whether expanded tampon shape affects VMB composition during, and in between menses. We will recruit 20 women from the University of Michigan, Ann Arbor to use Tampax® Pearl® Regular Tampons (expand into a rectangular prism-like shape) and Playtex® Gentle Glide® 360°® Regular Tampons (expand into a conical shape) for one menstrual cycle each, in a randomly assigned order. We will obtain twice-weekly self-collected vaginal swabs for a 2-3 week baseline window before the first menstrual cycle with an assigned tampon, followed by the two menstrual cycles with assigned tampon use, and finishing with one menstrual cycle with menstrual product use according to each subject's normal habits. DNA will be isolated from the vaginal swabs, and the bacterial 16S rRNA encoding genes will be amplified by PCR. Sequencing will be performed using the MiSeq Illumina platform, and analyzed to answer the above questions.

Outcomes and aims

- Primary Outcome: Change in relative abundance of *Lactobacillus* species from: baseline to the end of first menstrual cycle, baseline to the end of second menstrual cycle, and baseline to the end of third menstrual cycle (approximately 14 weeks)
- Secondary Outcome: Change in relative abundance of *Gardnerella vaginalis* from: baseline to the end of first menstrual cycle, baseline to the end of second menstrual cycle, and baseline to the end of third menstrual cycle (approximately 14 weeks)
- Exploratory Outcomes
 - To characterize intra-woman, during-menses changes in VMB composition caused by (see Methods – Study Design and Methods – Whole Community Analysis & Statistics sections for notes on causal inference) changing the expanded tampon shape of tampon used.
 - Hypothesis 1: VMB composition will vary between menses with Tampax® Pearl® Regular Tampon use and Playtex® Gentle Glide® 360°® Regular

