Tampon use because the different expanded shapes of the two tampons will alter the vaginal environment differently and thus promote growth of different taxonomic groups. The primary structural difference between Tampax® Pearl® Regular Tampons and Playtex® Gentle Glide® 360°® Regular Tampons is that, once inserted into the vagina, Tampax® Pearl® Regular Tampons expand axially into a rectangular prism-like shape, while Playtex® Gentle Glide® 360°® Regular Tampons expand radially into a conical shape. The radial expansion of the Playtex® Gentle Glide® 360°® Regular Tampons likely results in increased surface area of the tampon that is in contact with the vaginal epithelium as compared to the Tampax® Pearl® Regular Tampons. This may allow for increased absorption of menses by the Playtex® Gentle Glide® 360°® Regular Tampons as compared to the Tampax® Pearl® Regular Tampons, resulting in differing growth conditions in the vagina during Playtex® Gentle Glide® 360°® Regular Tampon use and Tampax® Pearl® Regular Tampon use.

- To characterize intra-woman, between-menses changes in VMB composition caused by (see Methods – Study Design and Methods – Whole Community Analysis & Statistics sections for notes on causal inference) changing the expanded shape of tampon used.
 - Hypothesis 2.1: Persistence of VMB changes observed during menses caused by changing the expanded shape of the tampon used will vary dependent on baseline VMB community type such that VMB changes will persist for greater time between menses in women with typically diverse VMB that confer reduced colonization resistance compared to a *Lactobacilli* dominated VMB [Borovkova 2011, Lopes 2011, Borges 2014, reviewed in Hickey 2012].
 - Hypothesis 2.2: Within women with *Lactobacilli* dominated baseline VMB, persistence of VMB changes observed during menses caused by changing expanded tampon shape will vary based on the degree of reduction of *Lactobacilli* abundance during menses such that changes resulting in greater reductions of *Lactobacilli* abundance will persist for greater time between menses.

Methods

Recruitment

- We will recruit 40 women from the University of Michigan, Ann Arbor during the Winter 2017 semester.
 - We will make an in-person announcement in Women’s Studies 400: Women’s Reproductive Health (taught by [name], Dept. of OB/GYN) according to the following script:

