 - Hello everyone, we are here to recruit forty healthy female students to participate in our study examining the impact of changing tampon use on the composition of the vaginal microbiota. The study period will consist of a baseline window after a subject’s last period and three full menstrual cycles. For the first two menstrual cycles, each subject will use Tampax® Pearl® Regular

Tampons and Playtex® Gentle Glide® 360°® Regular Tampons for one menstrual cycle each, in a randomly assigned order. For the third menstrual cycle, each subject will use menstrual products according to their normal habits. For the course of the study, approximately 4 months, subjects will self-collect vaginal swabs twice a week. These samples will be used for bacterial community analysis to assess the composition of the vaginal microbiota at each time point, and compare composition during periods using different tampons and determine how long these changes persist between periods. For the first two menstrual cycles, the study tampons and Always® Infinity® Regular Pads will be provided to subjects free of charge. Additionally, each subject will receive \$20. In order to be eligible to participate in this study, you must be at least 18 years old, have regular menstrual cycles that last 3-5 weeks with periods that last for at least 4 days, currently use tampons, and be in good general and vaginal health. You are ineligible to participate if you are pregnant or planning on becoming pregnant in the next 4 months, if you have difficulty using tampons, if you currently have or have had toxic shock syndrome (TSS), if you currently have a sexually transmitted infection (STI) or urinary tract infection (UTI), if are currently using antibiotics or antifungals or have used antibiotics or antifungals within the last month, or if you have an autoimmune condition. If you are interested in participating in this study, please email ([contact]) and then we will set up an enrollment meeting.

- We will also pass out flyers describing the objective of the study, the duration of subject participation, subject responsibilities, subject compensation, eligibility requirements, and exclusion criteria. It will also include the email address for setting up enrollment meetings. We will also post these flyers at the Michigan Union and other places around central campus.
- We will also post the study in UMHealthResearch.org.

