- We will respond to interest emails according to the following script in order to set up enrollment meetings with each interested student:
 - Dear [name],

Thank you for your interest in participating in this study. The next step is to set up an enrollment meeting at which you will be assigned a random study ID number, review the informed consent document for the study, give informed consent to participate in the study if you choose to, complete an online enrollment survey, and receive the tampons, pads, and vaginal swabs for the study. The following times are available for the enrollment meeting:

Monday 9:30 AM – 4:15 PM

Tuesday 1:30 PM – 4:00 PM
Wednesday 11:00 AM – 4:15 PM
Thursday 1:30 PM – 4:15 PM

Please respond to this email with your preferred day and time for the enrollment meeting. The meeting will take approximately 30 minutes.

Thanks

- At the enrollment meeting we will obtain informed consent from each student, assign a random ID number to the student, administer the baseline survey (assess eligibility, collects data on covariates (covered in Methods subsection Study Design)) on a lab computer using Qualtrics, review subject responsibilities with each student, and distribute study materials including 30 vaginal swabs, vaginal swab instructions, 30 collection day surveys, 24 Tampax® Pearl® Regular Tampons, 24 Playtex® Gentle Glide® 360°® Regular Tampons, 24 Always® Infinity® Regular Pads with wings to each subject. All research data will be kept in files that include the subject ID number, but not name or other information that is likely to allow someone other than the researchers to link the data to a subject. These files will be maintained in a password protected lab file manager. We will enroll the first 20 eligible students who schedule an enrollment meeting.
- Inclusion criteria: Subjects must be 18 years of age or older; have regular menstrual cycles lasting 21-35 days with menses for at least 4 days; be a current tampon user; be in self-reported good general health; and be in self-reported good vaginal health.

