- Distribution: Subjects will receive their study tampons and pads during their enrollment meeting.
- We will instruct subjects to use the study tampons as they normally would, not wear a tampon for more than 8 hours, not wear more than one tampon at a time, contact a doctor if they experience any serious adverse effects related to tampon use including TSS symptoms, remove the tampon prior to collecting a swab during menses, and use the pads in addition to the tampons if they so choose.

- We will provide subjects with written instructions from the tampon manufacturer on tampon use and ways to minimize risk of TSS.

Self-Collected Vaginal Swabs

- As in our pilot study, a double-headed, dry, rayon swab (Starplex Scientific, Inc., S09D) will be used for sample collection (HUM00098494).
- Swab distribution: Subjects will receive their vaginal swabs for the duration of the study (assumed duration of 15 weeks) during their enrollment meeting. If additional swabs are needed, subjects will pick them up from the first floor of MSRB1.
- Swab collection: Subjects will drop off their self-collected vaginal swabs on the first floor of MSRB1 during designated time windows each week; swabs will be stored in -80°C until analysis.
- Swabbing procedure: All swabs will include the following written instructions for self-collecting the vaginal swab (HUM00098494, HUM00086661):
 1. Read these instructions before starting.
 2. Locate a sterile swab labeled with your study ID number
 3. Write today's date (the day you used the swab) in the space provided on the swab label. Complete the short survey included with the swab. It is OK to collect a sample if you are menstruating, but if you are currently using a tampon, remove it before using the swab.
 4. Wash your hands.
 5. Remove the sterile swabs from the tube. Do not let them touch your body or any surface.
 6. Gently part your labia and insert both swabs approximately 2 inches into your vagina, imagining that you are pointing it towards your lower back.
 7. Gently turn the swabs 4 times, rotating the swab about 90 degrees with each turn.
 8. Remove the swabs taking care to not touch anywhere on your body.
 9. Place both swabs back into the tube.
 10. Place the tube into the plastic bag. Wash your hands.
 11. Return the swab to the first floor of MSRB1 during one of the designated time windows this week.

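### Return of cycle-3 swabs is at risk: students recruited in one semester must hand in swabs at one campus building for about 15 weeks, and no criterion asks whether they can

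*Combined protocol and SAP*

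**What the plan says.** All references are to the combined protocol and SAP.

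- **Recruitment.** "We will recruit 40 women from the University of Michigan, Ann Arbor during the Winter 2017 semester". The routes are a class announcement, campus flyers and a web listing ("We will also post the study in UMHealthResearch.org"). Places are first come, first served: "We will enroll the first 20 eligible students who schedule an enrollment meeting". (The mismatch between 40 and 20 does not bear on this point.)
- **Eligibility.** "Subjects must be 18 years of age or older; have regular menstrual cycles lasting 21-35 days with menses for at least 4 days". The other criteria concern tampon use, health, pregnancy, infection and medication. None concerns being able to attend the drop-off point.
- **Duration.** "Subjects will receive their vaginal swabs for the duration of the study (assumed duration of 15 weeks) during their enrollment meeting". Thirty swabs are issued at enrolment, and extra ones are fetched from the same building.
- **Return.** "Subjects will drop off their self-collected vaginal swabs on the first floor of MSRB1 during designated time windows each week". The instruction to each woman is "Return the swab to the first floor of MSRB1 during one of the designated time windows this week". No postal, courier or other route is described.
- **Study Design.** Baseline lasts 2-3 weeks. The two assigned tampons follow in random order, and the usual-habits control cycle always comes last.
- **Outcomes and aims.** The primary and secondary outcomes are changes from baseline to the end of cycle 1, "baseline to the end of second menstrual cycle, and baseline to the end of third menstrual cycle (approximately 14 weeks").
- **Whole Community Analysis & Statistics.** The intent-to-treat paragraph assumes complete follow-up. There is no rule for missing swabs and no expected return rate by window.

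**The concern.** A schedule of about 15 weeks that starts after a semester has begun will, for many women, end after that semester. Baseline and cycle 1 would fall in term. Any part of the schedule that falls outside term would be mostly cycle 3. A student who has gone home can still collect a swab, because she already holds the kit, but she cannot return it as the plan requires.

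The swabs most exposed are those at the end of cycle 3. They supply one of the three primary changes, one of the three secondary changes and the end of the only control window. Because cycle 3 is never randomised in position, its exposure is not balanced across the other conditions. The cycle-3 change could then rest on fewer women than the cycle-1 change. With 20 women, each one lost is 1/20 = 5% of the sample. Without a count of returns by window, a reader could not tell a trend across cycles from a change in who was still returning swabs.

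**Working it through.** **1. Reproduce the plan's duration.** Duration D = b + 3c, with baseline b in weeks and cycle length c in weeks. At 28-day cycles D = 2 + 12 = 14 or 3 + 12 = 15 weeks, matching the 14 weeks under Outcomes and the 15 weeks in the swab section. Swabs: 6 + 3 x 8 = 30, or 2 x 15 = 30, matching the number issued.

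**2. Extend to the eligible range.** For 21-day cycles and a 2-week baseline, D = 2 + 9 = 11 weeks. For 35-day cycles and a 3-week baseline, D = 3 + 15 = 18 weeks. Twice-weekly swabbing over 18 weeks needs 36 swabs, 6 more than are issued. Thirty swabs last 15 weeks. That woman's cycle 3 runs from week 13 to week 18, so she would run out during cycle 3 and have to resupply at the same building. (If the planned 8 swabs per cycle were a fixed count, 30 would be enough, but then swabbing would not be twice weekly in a 35-day cycle.)

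**3. Who finishes in term.** A woman enrolled e weeks into a T-week semester finishes in term only if e + b + 3c <= T. The documents give neither T nor the enrolment pace. Assumptions:
- T = 15, 16 or 17 weeks;
- e uniform over the first E = 1, 4 or 8 weeks;
- baseline starts at enrolment, with b uniform on 2-3 weeks;
- c uniform on 3-5 weeks and constant within a woman.

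At mid-range values (2.5 + 12 = 14.5 weeks) the latest enrolment that finishes in term is T - 14.5 = 0.5, 1.5 or 2.5 weeks.

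Simulated results, as ranges over T = 15 to 17:

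| Enrolment over | Share of cycle 2 in term | Share of cycle 3 in term | End of cycle 2 in term | End of cycle 3 in term |
|---|---|---|---|---|
| 1 week | 100% | 84-98% | 100% | 50-83% |
| 4 weeks | 99-100% | 60-86% | 93-100% | 26-58% |
| 8 weeks | 80-95% | 32-56% | 56-81% | 13-32% |

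Baseline and cycle 1 are at about 100% in every row.

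Hand check: 3c is uniform on 9 to 15, so P(finish in term) = mean of (T - 9 - s)/6, where s = e + b, as long as that ratio stays between 0 and 1. For E = 1, mean s = 0.5 + 2.5 = 3, which gives 3/6 = 0.50, 4/6 = 0.67 and 5/6 = 0.83. For E = 4, mean s = 4.5; T = 16 gives 2.5/6 = 0.42 and T = 17 gives 3.5/6 = 0.58.

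**4. Exposure is not loss.** If a share p of women leave at the end of term and return nothing afterwards, the share without an end-of-cycle-3 swab is p x (1 - in-term share). For T = 16 and E = 4 the out-of-term share is 1 - 0.417 = 0.583, or 11.7 of 20 women. Expected losses are 0 at p = 0, 2.9 women at p = 25%, 5.8 at p = 50% and 11.7 at p = 100%. The documents give no value for p.

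**5. Exposure depends on cycle length.** A woman with 21-day cycles needs 11-12 weeks and finishes inside a 15-week semester if enrolled in its first 3 weeks. A woman with 35-day cycles needs 17-18 weeks and cannot finish inside 15 or 16 weeks at all.

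**6. The tampon comparison.** Hypothesis 1 concerns swabs taken during menses, which opens each cycle. The first week of cycle 2 falls in term for 100% of women with enrolment over 1 or 4 weeks, and for 93-100% with enrolment over 8 weeks.

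**The case against.** The strongest objection is that the loss is a forecast. The documents give no semester length, enrolment pace, end to the drop-off windows, or statement that students leave. If nobody leaves, nothing is lost. This stands: a reader might infer that coverage does fall from baseline to cycle 3, but the documents support only that it may.

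Enrolment could also be quick. The meeting hours in the invitation email total 6.75 + 2.5 + 5.25 + 2.75 = 17.25 hours a week, enough for about 33 half-hour meetings, and only 20 places are on offer. This is why the 1-week row belongs in the table. Even there, the end of cycle 3 falls outside term for 17-50% of women.

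Two stronger readings should be set aside:
- A woman who loses her late cycle-2 swabs might seem to drop out of the tampon comparison. She does not. The during-menses swabs come at the start of the cycle; what suffers is the cycle-2 change and the between-menses aim.
- Uneven return might be taken to prove a biased trend. Outcomes are changes from each woman's own baseline and the distances tested are within subject, so bias would need leaving campus to be related to *Lactobacillus* change. The documents do not show that. What can be said is that precision in cycle 3 is at risk and that, because exposure rises with cycle length, any loss would not be random with respect to menstrual pattern.

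The plan has partial safeguards. Flyers and script state the duration, responsibilities are reviewed at enrolment, and reminders go out twice weekly. The reminders prompt collection rather than return, and the script does not name the building. The 100% pilot completion figure sits under the baseline survey, so it is not evidence on swab return.

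**Conclusion.** The point holds as a conditional risk to return of cycle-3 swabs. Five features of the plan create it: one-semester student recruitment, a single described in-person return point with same-week return, an 11-18 week commitment, no eligibility line on attendance, and an analysis that assumes complete follow-up. The size rests on assumed semester length and enrolment pace: the end of cycle 3 falls in term for anywhere from 13% to 83% of women across the cases examined. The actual loss cannot be stated, because it also depends on the unknown share who leave. The during-menses tampon comparison in cycles 1 and 2 is largely protected unless enrolment runs late. The point merits a cheap improvement; it does not invalidate the design.

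**What to change.** 1. For any enrolment still to come, add to the inclusion criteria, the recruitment script and the flyer: *expects to be able to drop off swabs at MSRB1 every week for the full study (11-18 weeks depending on cycle length)*. Ask this before booking the enrolment meeting, so that the 20 places go to women who can complete cycle 3.
2. Tabulate expected and received swabs by window (baseline, cycles 1, 2 and 3).
3. Report the three baseline-to-cycle changes in all available women and, as a sensitivity analysis, in the women who contribute all three. Restricting to women who contribute cycle 1 would not give a common set. The all-three set conditions on staying in the study and discards data, so it should accompany the main result and not replace it.

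The document is dated March 29, 2018, after the semester it names. If enrolment has closed, item 1 no longer helps, but items 2 and 3 still do.

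Cost: one eligibility line, one sentence in the script and flyer, one table and one extra analysis. The downside is that some interested students become ineligible and recruitment may be slightly slower.

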- Exclusion criteria: Respondents will be excluded if they are pregnant or are planning on becoming pregnant during the study; have difficulty using tampons; currently have, or have had TSS; currently have an STI; currently have a UTI; are currently using current antibiotics, or used antibiotics within 4 weeks prior to enrollment; are currently using current antifungals, or used antifungals within 4 weeks prior to enrollment; or have an autoimmune condition.

Study Design

- This study will be a longitudinal, interventional, case-crossover study with three exposure levels:
 - Experimental exposure levels: Each subject will use Tampax® Pearl® Regular Tampons and Playtex® Gentle Glide® 360°® Regular Tampons for one menstrual cycle each, in a randomly assigned order.
 - Control exposure level: Each subject will use menstrual products according to their normal habits for a third menstrual cycle.
 - A case-crossover design ensures exchangeability between treatment windows within each subject for all time invariant characteristics. Under exchangeability and the assumptions of an intent-to-treat analysis (covered in Methods – Whole Community Analysis &

Statistics), the actual outcome observed under one treatment for an individual equals the counterfactual outcome under that treatment for that individual, so association between expanded tampon shape and VMB composition represents a causal relationship. This study design and the intent-to-treat analytic strategy will allow us to make causal inference in reference to the effect of expanded tampon shape on VMB composition.

- Vaginal swabs will be self-collected by each subject twice weekly for four different exposure windows (Fig. 1):
 - A 2-3 week baseline window after the last menstrual period prior to enrollment; 4-6 baseline samples per subject.
 - One menstrual cycle using the Tampax® Pearl® Regular Tampons; 8 samples.
 - One menstrual cycle using Playtex® Gentle Glide® 360°® Regular Tampons; 8 samples.
 - The final menstrual cycle with menstrual product use according to the subject's normal habits; 8 samples for the subject's normal habits.

[figure not shown]

Figure 1: Study design.

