- Justification for choice of tampons A and B: The primary structural difference between Tampax® Pearl® Regular Tampons and Playtex® Gentle Glide® 360°® Regular Tampons is that, once inserted into the vagina, Tampax® Pearl® Regular Tampons expand axially into a rectangular prism-like shape (Fig. 2C), while Playtex® Gentle Glide® 360°® Regular Tampons expand radially into a cone-like shape (Fig. 3C). The radial expansion of the Playtex® Gentle Glide® 360°® Regular Tampons likely results in increased surface area of the tampon that is in contact with the vaginal epithelium as compared to the Tampax® Pearl® Regular Tampons. This may allow for increased absorption of menses by the Playtex® Gentle Glide® 360°® Regular Tampons as compared to the Tampax® Pearl® Regular Tampons, resulting in differing growth conditions in the vagina during

Playtex® Gentle Glide® 360°® Regular Tampon use and Tampax® Pearl® Regular Tampon use. Both tampons are inserted with a plastic applicator, and both are made of a cotton/rayon blend. The only other substantial structural difference between the two is that the Tampax® Pearl® Regular Tampons have a braided string (Fig. 2B) while the Playtex® Gentle Glide® 360°® Regular Tampons have a straight, 2 strand string (Fig 3A). Tampax® Pearl® reports that the braided string is designed to stop tampon leaks, and that it can hold up to 12 drops of fluid in addition to the volume held by the tampon (Fig. 2D). We do not anticipate this difference to substantially alter the growth conditions in the vagina because any contact between the string (braided or not) and the vaginal epithelium will be much less than that between the actual tampon and the vaginal epithelium. Another reason for choosing these tampons is that, for the past 6 years (2011-2016), Tampax® and Playtex® brand tampons have been the two most used tampon brands in the US [Experian 2016]. Examining how these tampon brands impact VMB composition will increase the generalizability of the study findings, as compared to if we selected other tampon brands.

- Pad: Always® Infinity® Regular Pads with wings (Fig. 4)
 - <http://always.com/en-us/shop-products/menstrual-pads/infinity-pads-with-flexfoam/always-infinity-regular-pads-with-wings>
 - \$0.31 per pad on amazon prime; 4.4 stars
 - $2 \text{ pads/day} * 12 \text{ days} = 24 \text{ pads} * 20 \text{ subjects} = 480 \text{ pads} *$
 $\$0.31/\text{pad} = \148.80

Figure 4: Always® Infinity® Regular Pads with wings.

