- Covariate data collection with each swab: We will provide a short survey with each swab on which subjects will record whether the swab was collected during menses as well as any changes in sexual activity, hygiene, medication use, general health, vaginal health, contraception use, pregnancy, menses since the baseline study or prior swab.
- We will remind subjects to collect swabs with twice-weekly text messages, emails, or phone calls based on preference.

Whole Community Analysis & Statistics

- DNA will be isolated from vaginal swab samples using a PowerMag Soil DNA isolation kit (Mo Bio Laboratories, Inc.) and an epMotion robot (Eppendorf epMotion 5075). The DNA samples will be submitted to the University of Michigan

Center for Microbial Systems Laboratory for amplification and sequencing of the V4 region of the 16S rRNA gene. The V4 region of the bacterial 16S rRNA gene will be amplified using dual-indexing sequencing strategy and sequenced on the Illumina MiSeq platform as described by Kozich et al. and Seekatz et al. After sequencing is completed, the 16S rRNA gene sequences will be processed and analyzed using the mothur software (version 1.34.3) and MiSeq SOP (http://www.mothur.org/wiki/MiSeq_SOP). Following sequence processing and alignment to the SILVA reference alignment [Preusse 2007], sequences will be binned into operational taxonomic units (OTUs) of 97% sequence identity. In our preliminary studies, we were able to detect and distinguish 6 different types of *Lactobacillus* among the top OTUs (>2% in at least 1 sample) from vaginal swab samples using an OTU definition of 3% sequence difference with sequences from the V4 region of the 16S rRNA gene. Relative abundances of OTUs will be calculated and we will test the dependence of within subject θ_{YC} distances on expanded tampon shape using Mann-Whitney tests or Kruskal-Wallis test, as dictated by the number of comparisons. Principal components analysis (PCoA) will be used to visualize θ_{YC} distances between samples within subjects. The same analysis protocol was used in our previous studies (HUM00098494, HUM00086661).

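### The normal-habits cycle is counted as a third exposure level but is always last and never randomised, so during-menses comparisons with it cannot be separated from cycle order

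*Combined protocol and SAP*

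**What the plan says.** Methods – Study Design describes a "longitudinal, interventional, case-crossover study with three exposure levels". The two study tampons are used "for one menstrual cycle each, in a randomly assigned order". The third level is habitual use: "Each subject will use menstrual products according to their normal habits for a third menstrual cycle". The list of swab windows places it last for everyone: "The final menstrual cycle with menstrual product use according to the subject's normal habits". A baseline window of 2-3 weeks, after the last period before enrolment, comes before the first assigned cycle.

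The same section then argues that windows within a woman are exchangeable for characteristics that do not vary with time. From this it concludes that an association between expanded tampon shape and the microbiota is causal. The intent-to-treat item under Whole Community Analysis & Statistics repeats the conclusion. Neither place confines it to the two randomised cycles.

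On habitual products, each woman must "be a current tampon user", and no exclusion criterion removes habitual users of either study product. The Menstrual Products section notes that "Tampax® and Playtex® brand tampons have been the two most used tampon brands in the US". The baseline survey asks about usual product types, brand and absorbency, but no analysis use is given. The survey issued with each swab asks about menses and about changes in health, hygiene, medication and similar items. It does not list the menstrual product used.

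The analysis tests whether within-subject θYC distances depend on expanded tampon shape, "using Mann-Whitney tests or Kruskal-Wallis test, as dictated by the number of comparisons". The plan does not name the groups, and it gives no period term, carry-over term or washout. The primary and secondary outcomes each include the change from baseline to the end of the third cycle.

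**The concern.** A control exposure that everyone receives last shares its position with everything else that happens last: time on study, season and term, fatigue with sampling, and any residual effect of the study-tampon cycle just before it. Randomising the other two cycles does not help. Cycle order varies with time by definition, so an exchangeability argument about time-invariant characteristics does not reach it.

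The exposure itself is also undefined. A woman's usual product could be one of the two study tampons, another line or absorbency of the same brand, another brand, pads, or a mixture. Such a cycle has no single expanded shape, which is the factor that the analysis tests.

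At stake is how a difference involving cycle 3 would be read. Under the plan's causal wording, a pure change in the third cycle could be reported as an effect of the product.

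**Working it through.** The plan gives no alpha, power, effect size or sample-size calculation, so there is no figure to reproduce. The checks below concern what the design can identify.

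**1. Estimability (no assumed values for variance or effect).** Inputs from Recruitment and Study Design: 20 women, three cycles each, sequences A-B-H and B-A-H (A = Tampax, B = Playtex, H = normal habits). The model is outcome = subject + cycle + product.

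- Parameters: 20 subjects + 2 cycle contrasts + 2 product contrasts = 24.
- Rank of the design matrix: 23. The indicator for cycle 3 and the indicator for H are the same column.
- B − A is estimable. H − A and H − B are not.
- For comparison, if H were also randomised over the three positions (six sequences, 20 women), the rank would be 24 of 24 and all three contrasts would be estimable.

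**2. Does change from baseline repair this?** No. With a common baseline for each woman, (H − baseline) − (A − baseline) = H − A, which is the same unidentified contrast.

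**3. Does the baseline window help in another way?** In part, and only for between-menses data. Number the windows 0 (baseline), 1, 2 and 3. The habitual-use windows have mean position (0 + 3)/2 = 1.5, and the study cycles have mean position (1 + 2)/2 = 1.5. A linear trend over equally spaced windows would therefore cancel in the average of the habitual windows minus the average of the study cycles. It would not cancel if the trend is non-linear or if there is carry-over. Spacing is also only roughly equal, because the baseline window is 2-3 weeks and a cycle is 21-35 days. During menses there is no bracketing at all: the baseline window starts after a period ends and precedes the first assigned cycle, so habitual-product menses are sampled only in cycle 3.

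**4. What a three-group test would do.** This is an illustration and applies only if cycle 3 is the third group. Assumed: 20 women, one normally distributed value per woman and cycle, total SD 1, two-sided alpha 0.05, no product effect, a shift in cycle 3 only, and 10,000 runs per row. The values stand in for a generic outcome. They are not θYC distances.

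| Within-woman correlation | Cycle-3 shift (SD) | Kruskal-Wallis rejects | Friedman rejects | Paired A-B (Wilcoxon) rejects |
|---|---|---|---|---|
| 0 | 0 | 4.9% | 5.4% | 4.9% |
| 0 | 0.5 | 31.9% | 26.3% | 4.8% |
| 0 | 1.0 | 88.0% | 76.7% | 4.6% |
| 0.5 | 0 | 0.4% | 5.4% | 4.9% |
| 0.5 | 0.5 | 21.6% | 47.4% | 5.0% |
| 0.5 | 1.0 | 93.0% | 97.5% | 4.8% |

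A matched three-group test (Friedman) also rejects because of the shift, so changing the test does not cure the aliasing. The A-B comparison stays near 5% in every row.

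**The case against.** The strongest reply is that the plan never states a test against normal habits. Hypotheses 1, 2.1 and 2.2 all concern changing the expanded shape. The causal sentences are worded around shape, and a normal-habits cycle has no assigned shape. The comparison that answers Hypothesis 1 is randomised and is untouched by where the control sits. The baseline survey already records usual brand and absorbency, and a closing return-to-habit cycle is a legitimate descriptive choice.

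Much of this stands. A reader might infer that the plan specifies a three-group test including the control. It does not. Three named exposure levels and a test needed only for three or more groups make that reading natural, but the groups are left open, so the simulated rates are conditional on it.

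A reader might also infer that cycle 3 is wholly confounded with time in all the data. For between-menses samples that goes too far, because the baseline window offers the partial bracketing shown in the working. It does not help during menses.

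What does not stand is that the wording already limits the claim. The causal paragraph follows directly from the three exposure levels without excluding the third, and cycle 3 is part of the primary and secondary outcomes. The baseline survey records the usual product, not what was actually used in cycle 3.

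**Conclusion.** The concern holds for contrasts between either study tampon and normal habits. During menses these are completely aliased with the third cycle, and carry-over from the preceding study cycle cannot be separated from them. That conclusion rests only on the stated sequences. The possible size of a false finding depends on an assumed shift and on cycle 3 entering the Kruskal-Wallis test: about 22% to 32% rejection at 0.5 SD and 88% to 93% at 1 SD, with no product effect.

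The randomised Tampax-Playtex contrast is not affected by the control's position.

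A reader might go further and infer that many women will repeat a study product in cycle 3, and then compute how far the control contrast shrinks. The documents do not support this. They rank brands nationally, give no market share, and say nothing on the share using these particular lines and absorbencies. Nor would the effect be simple shrinkage, because some women may habitually use the other study tampon. Overlap is possible and its extent is unknown. The supportable statement is that the control is undefined as an exposure.

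This should be corrected, but it does not undermine the study's main randomised comparison.

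**What to change.** - **Study Design, and the analysis and intent-to-treat items under Whole Community Analysis & Statistics:** limit the confirmatory test and the causal statement to the within-woman Tampax versus Playtex contrast over the two randomised cycles, and name those two groups as the ones compared.
- **Study Design:** label cycle 3 a non-randomised, descriptive return-to-habit window. Report the third-cycle part of the primary and secondary outcomes on that footing.
- **Survey issued with each swab:** add one line for the menstrual product used. Report cycle 3 by product actually used (Tampax, Playtex, other tampon, pad or other, none), with the pre-assignment baseline window alongside for between-menses data. If collection is already complete, the usual product from the baseline survey is the available proxy and should be described as such.

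The cost is some wording and one survey line. The loss is a formal test against usual habits. During menses this design could not separate such a test from time in any case. Recovering it would need the normal-habits cycle to be randomised in position as well, which is a different design.
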